	Visit 1 Screening Visit	Visit 2 Baseline Visit	Visit 3 3 months	Visit 4 6 months
Informed consent	X			
Ocular and medical history, including contact lens wear history	X	X	X	X
CLDEQ-8 Questionnaire	X	X	X	X
SPEED Questionnaire	X	X	X	X
NPSI Questionnaire	X	X	X	X
Visual acuity	X	X	X	X
Slit lamp examination	X	X	X	X
Capillary tear collection	X	X	X	X
Tear break-up time		X	X	X
Corneal staining		X	X	X
Conjunctival and lid wiper staining		X	X	X

Schirmer's I Test	X	X	X	X
Meibography with Oculus Keratograph	X			
Study drug or placebo dispense	X	X	X	
Study drug collection		X	X	X
Expected Duration	45 mins	60 mins	60 mins	60 mins

B. Sample Size and Analysis

LTB₄ values will serve as a primary biological outcome for judging if HydroEye® is able to improve ocular surface health. Work from Masoudi et al. suggests that LTB₄ is significantly different between symptomatic (0.32 ± 0.06 ng/mL) and asymptomatic (0.17 ± 0.04 ng/mL) contact lens wearers. A 0.06 ng/mL difference (equivalent to one standard deviation) in LTB₄ concentration will be considered a meaningful improvement in LTB₄ concentration. Thus, 16 subjects per group will be needed to determine if there is no difference in LTB₄ concentration between groups at the final outcome visit (power = 80%; alpha = 0.05). After adjusting for 10% dropout, a total sample size of 36 subjects will be needed to determine if there is a statistical difference between subject groups.

CLDEQ-4 scores (Rasch validated version; max score of 18) will serve as the primary outcome for judging if HydroEye® is able significantly improve contact lens comfort.²⁷ Data from Pucker et al. suggests that the average contact lens wearer has a mean CLDEQ-4 score of 7.6 ± 3.8 .²⁷ A 4-point difference in CLDEQ-4 scores will be considered a meaningful improvement in CL comfort. Therefore, 19 subjects per group will be needed to determine if there is no difference in contact lens comfort between the two groups at the final outcome visit (power = 90%; alpha = 0.05). After adjusting for 10% dropout and subject withdrawals, a total sample size of 42 subjects will be needed to determine if there is a statistical difference in contact lens comfort scores between subject groups. Since the sample size based upon CLDEQ-4 is larger, 42 subjects will be recruited.

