An additional 10 subjects are being requested to account screen fails, and 8 more subjects are being requested for assay protocol development. Therefore, this study is requesting a maximum of 60 subjects. If additional subjects are not needed to account for screen fails, recruitment will be stopped accordingly.

Baseline data of the active and placebo groups will be analyzed at study completion. Primary and all secondary outcomes will be compared to baseline and between groups. SPSS will be used for all analysis.

C. Objectives

CO-PRIMARY OBJECTIVE

To assess changes in comfortable contact lens wear time and subjective symptom severity (CLDEQ-4) in response to HydroEye® supplementation in those who experience contact lens discomfort

SECONDARY OBJECTIVE

To assess changes in LTB₄ levels in response to HydroEye® supplementation in those who experience contact lens discomfort

D. Endpoints

CO-PRIMARY ENDPOINTS

Mean change in the difference between overall wear time and comfortable wear time at 6 months

Mean change in CLDEQ-4 scores at 6 months

SECONDARY ENDPOINTS

Mean change in LTB₄ levels at 6 months

Mean change in SPEED scores at 6 months

Mean change in NPSI scores at 6 months

Mean change in TBUT at 6 months

Mean change in Schirmer I at 6 months

Mean change in corneal staining at 6 months

Mean change in conjunctival staining at 6 months

Mean change in lid wiper epitheliopathy at 6 months

Mean change in tear cytokine levels (RayBiotech Human Inflammation Array Q3) at 6 months

E. Inclusion Criteria

[figure not shown]
1. Age \geq 18 years
2. Provide informed consent and authorization to disclose protected health information
3. Willing to follow study protocol
4. Habitual, contact lens-corrected visual acuity of at least 20/30 in each eye
5. Wear soft contact lenses as daily wear for at least 6 hours per day and at least 5 days per week for the past 30 days
6. Have at least a 2-hour difference between overall wear time and comfortable wear time of contact lenses
7. Have symptoms consistent with Contact Lens Dry Eye based on CLDEQ-8 (score \geq 12)
8. Increased severity of dry eye symptoms with contact lens wear by at least 25% as determined by patient self-report

9. Clinical assessment that contact lens material, fit, prescription, and care system are not reasons for contact lens discomfort
10. Demonstrate at least 80% compliance in completion of daily electronic diary (submitted through Qualtrics Research Suite) between V1 and V2

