11. Willing to discontinue use of any current dry eye treatment (including use of commercial hygiene masks, and except for artificial tears) for 4 weeks before randomization and during the course of the 6-month study.

F. Exclusion Criteria

1. Meibomian gland dropout $\geq 75\%$ in either eyelid
2. Any changes to the contact lens material, fit, prescription, or care system in the 30 days preceding enrollment or anticipates needing to make changes during the course of the study
3. Any systemic disease known to be associated with dry eye
4. Any significant ocular surface abnormality that could be associated with ocular surface discomfort, such as ectropion, entropion, trichiasis, infection, severe allergic conjunctivitis, severe eyelid inflammation, etc.
5. Any overnight wear of contact lenses
6. Any previous corneal surgery, including all types of corneorefractive surgery
7. Have temporary and/or permanent punctal plugs inserted
8. Use of supplemental fish oil, or seed oils from borage, evening primrose, sea buckthorn, flaxseed, or black currant within the last 60 days
9. Routine, usual dietary intake of more than 8 oz. of cold-water fatty fish (tuna, salmon, mackerel, sea bass, sardines or herring) per week).
10. Use of anticoagulant therapy or regular, daily use of aspirin, NSAIDs, or steroid medications within the past 30 days, or a history of easy bruising
11. Allergy or intolerance to fish or any ingredients contained in the active or placebo formulas [See appendix or ingredient list]
12. Participation in a clinical trial in the past 30 days
13. Current pregnancy or breast feeding as indicated by self-report

III. TIMELINE AND REPORTING

IV. BUDGET

The following budget outlines the estimated costs associated with the proposed clinical trial.

Item	Unit Cost	Total
Clinical Assessment		
Consumables (fluorescein, lissamine green, alcohol pads, charts, Schirmer strips, etc.)	-----	\$550.00
Salaries		
Clinician (3.75 h/subject * 55 subjects = 112.5 clinician hours)	\$150.00/hour	\$30,937.5
Study coordinator (0.5 hours/visit * 120 visits = 60 coordinator hours)	\$50.00/hour	\$3,000.00
Subject Compensation		
Subject Visit (\$20 for V1; \$40 for each V2-V4)	\$140.00/subject	\$4,200.00
Laboratory Assessment		
RayBiotech Human Dry Eye Disease Array Q1 (32-50 sample kit, Qty 3)	\$4,694.00	\$14,082
Enzolife Sciences LTB4 ELISA Kit (50 sample kit, Qty 3)	\$559	\$3,501
Other		
Protocol development and IRB review	\$2,500.00	\$2,500.00

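### The tear-cytokine endpoint and the budget name different arrays, and the multi-analyte panel has neither false-positive control nor an exploratory label

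*Combined protocol and SAP*

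**What the plan says.** The endpoint list in Section II.D ends its secondary endpoints with "Mean change in tear cytokine levels (RayBiotech Human Inflammation Array Q3) at 6 months". The product name is the endpoint's only definition. The text gives no analyte list, analyte count, key cytokine or summary score.

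The laboratory lines of the budget (Section IV) cost "RayBiotech Human Dry Eye Disease Array Q1 (32-50 sample kit, Qty 3" and no other cytokine array.

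The analysis rule for all outcomes is in Section II.B: "Primary and all secondary outcomes will be compared to baseline and between groups. SPSS will be used for all analysis". It names no test, adjustment, hierarchy or false discovery rate. A significance level appears only in the two sample-size statements of that section, "power = 80%; alpha = 0.05" for LTB₄ and "power = 90%; alpha = 0.05" for CLDEQ-4. The panel is listed as secondary, in the same list as LTB₄, and is nowhere called exploratory.

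**The concern.** There are two linked problems.

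- **Which panel.** The product name alone defines this endpoint, so two product names leave it open which analytes make up the outcome. If the costed array were run without an amendment, the results would not be those of the array that the endpoint names.
- **How many tests.** One line in the endpoint list stands for as many tests as the array has analytes. The analysis rule asks for a comparison with baseline as well as one between groups. With nothing said about multiplicity, a report could present one or two nominally significant cytokines as an effect of the supplement when chance alone would often produce them. Such a result would be attractive here because it would seem to support an anti-inflammatory mechanism.

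**Working it through.** **1. The plan's own figures.** No figure is stated for the cytokine endpoint, so the check starts from the two sample sizes in Section II.B. With n per group = 2(z₁₋α/₂ + z₁₋β)²(SD/δ)² and two-sided alpha 0.05 (sidedness is not stated, but two-sided reproduces the plan):

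- CLDEQ-4: δ = 4 and SD = 3.8 ("A 4-point difference in CLDEQ-4 scores will be considered a meaningful improvement in CL comfort"; "mean CLDEQ-4 score of 7.6 ± 3.8"), power 90%: 2 × (1.960 + 1.282)² × (3.8/4)² = 18.97, so 19 per group, as stated.
- LTB₄: δ = 0.06, equal to 1 SD, power 80%: 2 × (1.960 + 0.842)² = 15.70, so 16 per group, as stated.

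The panel enters neither calculation.

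**2. The two array names.** The endpoint list has Human Inflammation Array, Q3. The budget has Human Dry Eye Disease Array, Q1. Panel name and suffix both differ, so a single typing slip is unlikely. The array line multiplies out (3 × $4,694 = $14,082), but other budget lines do not fit together:

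- The clinician line states 112.5 hours for 3.75 h × 55 subjects, but the product is 206.25; 112.5/3.75 = 30 subjects.
- Coordinator visits give 120/4 = 30 subjects, and compensation gives $4,200/$140 = 30. The trial randomizes 42.
- The LTB₄ kit line prints $3,501, but 3 × $559 = $1,677.

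The budget therefore mixes versions. It cannot settle which array is intended, nor can it be used to dismiss the difference.

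**3. False positives if every analyte is tested.** The documents give no analyte count, so m is an assumption. For m independent analytes, each tested once between arms at 0.05 with no true effect, the chance of at least one false positive is 1 − 0.95^m and the expected number is 0.05m.

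| m (assumed) | At least one false positive | Expected number |
|---|---|---|
| 5 | 22.6% | 0.25 |
| 10 | 40.1% | 0.5 |
| 20 | 64.2% | 1.0 |
| 40 | 87.1% | 2.0 |

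Positive correlation between analytes lowers the middle column but not the last. One baseline comparison per analyte doubles the number of tests. At m = 10 that would give 1 − 0.95^20 = 64.2% if all were independent, which is only a rough guide because the two comparisons share data.

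**4. Cost of control.** Bonferroni is the stricter bound. With 19 per group and a 1 SD effect, approximate power is Φ(√(19/2) − z), where √(19/2) = 3.082:

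- Unadjusted, alpha 0.05: Φ(3.082 − 1.960) = 87%.
- m = 10, alpha 0.005: Φ(3.082 − 2.807) = 61%.
- m = 20, alpha 0.0025: Φ(3.082 − 3.023) = 52%.
- m = 40, alpha 0.00125: Φ(3.082 − 3.227) = 44%.

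T-test versions of the last three are lower: 54%, 45% and 36%. Benjamini-Hochberg at 5% rejects everything that Bonferroni rejects and possibly more, so it costs no more than this. Its exact power depends on how many analytes truly change, which is unknown.

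**The case against.** The case on the other side is substantial.

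- **The endpoint section should govern.** The budget describes itself as estimated costs and is visibly part-updated. A stale kit name is a simple explanation, and a named commercial array would ordinarily fix its own panel. This stands as a reason not to read much into the mismatch. It does not remove the need to make the two places agree.
- **A reader might infer that the endpoint cannot be measured with the kit purchased.** The documents do not support that. A budget line is not a purchase, and neither panel's contents are given, so the overlap could be large or small.
- **A reader might infer that the analytes will be chosen after the results are seen.** That does not follow. A change of array made before assay, and documented, is an amendment and not data-driven selection.
- **A reader might infer that the plan commits to testing each analyte at 0.05.** It does not say so, because alpha is tied only to the sample-size calculations. The gap is silence on how the panel will be judged, and the percentages show what unadjusted testing would do under assumed counts.
- **The panel is supportive.** It is the last of nine secondary endpoints, and the stated secondary objective names only LTB₄. Unadjusted biomarker panels are common in small trials. That is a fair argument for an exploratory label, but the plan does not apply one.

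**Conclusion.** The concern holds as a modest, inexpensive correction. Two things are established from the text: the endpoint list and the budget name different arrays, and a multi-analyte secondary endpoint carries neither a false-positive rule nor an exploratory label.

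The size of the inflation cannot be fixed from the documents. The 40% to 87% range depends on assuming 10 to 40 analytes, independence, and a separate between-arm test of each at 0.05. With fewer or positively correlated analytes the chance is lower.

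It would be wrong to conclude that the trial's main result is at risk. The co-primary endpoints do not use the array, and the sample size of 42 was derived without it. What is exposed is any claim that the supplement changed a particular tear cytokine.

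**What to change.** Before any study sample is assayed:

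1. Name the same array in Section II.D and in the laboratory lines of Section IV, and attach its analyte list as the prespecified family.
2. Base inference on the between-arm 6-month difference for each listed analyte, with Benjamini-Hochberg control at 5% across the list. Present comparisons with baseline as description only.
3. Report every analyte tested, with estimates and intervals, and state how many there were.

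If formal control is not wanted, label the panel exploratory, report it in full in the same way, and claim no effect from single analytes.

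The cost is a wording change in two places, an attached list, a few lines of analysis and possibly a different kit order. The statistical downside is less power to declare any single cytokine, bounded by the Bonferroni figures above. The sample size need not change.

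### LTB₄ and tear cytokines are defined as plain mean change in level; a baseline-adjusted comparison on the log scale would keep more power, mainly through the adjustment for LTB₄ and through the log scale for the cytokines

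*Combined protocol and SAP*

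**What the plan says.** Section II.D lists two biomarker endpoints among the secondary endpoints: "Mean change in LTB₄ levels at 6 months" and "Mean change in tear cytokine levels (RayBiotech Human Inflammation Array Q3) at 6 months". Section II.B fixes the LTB₄ target on the concentration scale: "A 0.06 ng/mL difference (equivalent to one standard deviation) in LTB₄ concentration will be considered a meaningful improvement". It sizes LTB₄ on a different contrast from the endpoint, the level at the last visit: "16 subjects per group will be needed to determine if there is no difference in LTB₄ concentration between groups at the final outcome visit".

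The analysis text in II.B amounts to "Primary and all secondary outcomes will be compared to baseline and between groups. SPSS will be used for all analysis". It names no test, model, covariate or transformation. The documents give a mean and SD for LTB₄ only; they give none for any cytokine.

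**The concern.** A change score subtracts the whole baseline value, whatever the baseline to follow-up correlation. When that correlation is moderate, this adds noise that a regression on baseline would avoid. Separately, if a product lowers a marker by a percentage and the marker is right-skewed, the raw scale gives subjects who start high more weight than the rest, and a consistent percentage fall is harder to detect.

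LTB₄ is the only outcome named in the secondary objective, and with the cytokine array it is the trial's evidence on inflammation. With about 19 completers per arm there is little room to lose power through the choice of analysis. Leaving the scale unstated also means that it could be chosen after the data are seen.

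**Working it through.** **1. The plan's own figure.** II.B gives a difference of 0.06, an SD of 0.06, 80% power and alpha 0.05 (two-sided reproduces the result).

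n = 2 × (1.96 + 0.84)² × (0.06/0.06)² = 15.7, so 16 per group. Then 32/0.9 = 35.6, so 36 in total. Both match. (The t-based n is 17.)

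**2. Completers.** 42 recruited at 1:1 is 21 per arm; 21 × 0.9 = 18.9, about 19.

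**3. What the LTB₄ figures say about scale.** The plan cites "symptomatic (0.32 ± 0.06 ng/mL) and asymptomatic (0.17 ± 0.04 ng/mL) contact lens wearers".

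- Relative SD: 0.06/0.32 = 18.8%; 0.04/0.17 = 23.5%.
- SD ratio 0.06/0.04 = 1.5; mean ratio 0.32/0.17 = 1.88. The implied exponent is ln 1.5 / ln 1.88 = 0.64, so spread grows with level, but less than proportionally.
- Log-SD for symptomatic wearers, the population enrolled: √ln(1 + 0.1875²) = 0.186.
- Target as a ratio: (0.32 − 0.06)/0.32 = 0.81.

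**4. LTB₄ power.** Simulation of 40,000 trials, 19 per arm, log-normal values, log-SD 0.186, ratio 0.81, two-sided 0.05. The correlation is not in the documents, so a range is shown.

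| Assumed correlation | Raw change | Log change | Raw, baseline-adjusted | Log, baseline-adjusted |
|---|---|---|---|---|
| 0.3 | 75.6% | 81.0% | 92.8% | 93.2% |
| 0.5 | 87.8% | 92.0% | 96.5% | 96.8% |
| 0.7 | 98.0% | 99.1% | 99.5% | 99.6% |

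At correlation 0.5 the total gain is 96.8 − 87.8 = 9.0 points, of which 96.5 − 87.8 = 8.7 come from baseline adjustment and 0.3 from the log scale. At 0.3 the total is 17.6 points; at 0.7 it is 1.6.

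Hand check on the log scale at 0.5: the effect is |ln 0.8125| / 0.186 = 1.12 SD. The signal for log change is 1.12 × √(19/2) = 3.44, because the SD of change is √(2 × (1 − 0.5)) = 1 times the SD. With adjustment the residual SD is √(1 − 0.5²) = 0.866 times the SD, so the signal is 3.44/0.866 = 3.97. The normal approximation gives about 93% and 98%, in line with the simulated 92.0% and 96.8%.

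**5. If LTB₄ is normal and the effect is a constant 0.06 ng/mL.** The last-visit comparison has 85.1% power raw and 84.1% log. A baseline-adjusted comparison of such data shows the same loss of about 1 point.

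**6. Cytokines.** Every input here is an assumption: log-normal values, correlation 0.5, 19 per arm. Figures move by a point or so between simulation runs.

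| Assumed log-SD, fall | Raw change | Log change | Raw, adjusted | Log, adjusted |
|---|---|---|---|---|
| 0.47, 30% | 48% | 63% | 68% | 73–74% |
| 0.8, 50% | 41% | 74% | 69% | 84% |
| 1.0, 50% | 26% | 55% | 44% | 65% |
| 1.5, 60% | 13% | 46% | 24% | 55% |

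The log scale adds 15 to 33 points to a change score, and about 6 to 31 points when both analyses adjust for baseline.

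**The case against.** The strongest reply is that the plan never says raw and unadjusted. It names no method, so an adjusted or log analysis is not barred. That is fair, but the endpoint wording and the ng/mL target point to raw change, and an open choice of scale is itself a reason to settle it in advance.

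Second, the LTB₄ sample size rests on the last-visit comparison, where scale hardly matters: 91.3% raw against 91.9% log at correlation 0.5. This stands. On that reading the gain from the proposed analysis is 96.8 − 91.3 = 5.5 points, again mostly from adjustment. Either way raw LTB₄ power at correlation 0.5 exceeds the planned 80%, so a null LTB₄ result could not simply be blamed on the scale. At an assumed correlation of 0.3, raw change does fall below 80%.

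Third, the large cytokine losses follow from chosen inputs. This also stands. With little dispersion the gap closes: at log-SD 0.3 and a ratio of 0.75, the last-visit comparison has 80% power raw and 82% log.

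A reader might go further and infer three things that the documents do not support:

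- **That a few high-baseline subjects dominate LTB₄.** At the symptomatic figures, the two highest of 19 (10.5% of an arm) supply about 19 to 22% of the raw-change sum of squares. That is more than their share, but not dominance.
- **That the LTB₄ figures prove proportional variation.** The two SDs come from different populations, only one of which is enrolled, and the relative SD falls as the mean rises.
- **That raw change could create false differences.** Under no effect, the simulated rejection rate of the raw-change test is 5.0% at log-SD 0.186, about 4% at 1.0 and 3.1% at 1.5, so it is not inflated.

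**Conclusion.** The concern holds in a limited form. Comparing unadjusted mean change in level loses power that a baseline-adjusted log-scale comparison would keep, using data already collected.

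For LTB₄ the loss is about 9 points at an assumed correlation of 0.5 (1.6 at 0.7, 17.6 at 0.3). It is almost wholly a matter of baseline adjustment. The log scale adds under 1 point, and costs about 1 point if the data are normal and the effect additive.

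For the cytokines the log scale itself could matter a good deal, but the size rests on assumed dispersions and effects and cannot be read across from the LTB₄ figures.

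The severity is minor to moderate. These are secondary endpoints, and the sample size of 42 is set by CLDEQ-4.

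**What to change.** In II.B and II.D, before unmasking, add text such as: *LTB₄ and each cytokine will be compared between arms on the natural log of the 6-month value, adjusted for the natural log of the baseline value. The active/placebo geometric mean ratio will be reported with its 95% CI. Mean change on the original scale (ng/mL for LTB₄) will be shown as a descriptive result.* Give the LTB₄ target as a ratio, 0.26/0.32 = 0.81, beside the 0.06 ng/mL. Because zero and undetectable values have no logarithm, state also how values below the assay limit will enter the analysis; the documents give no limit.

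The cost is a few sentences, with no new subjects, visits or assays. The downsides are small: results read as ratios, which the ng/mL row offsets, and LTB₄ could lose about 1 point of power if its effect is additive.

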
VI. APPENDIX

Combined Ingredient List – Active and Placebo Formulas

CONFIDENTIAL STUDY MATERIALS – FOR INVESTIGATOR REFERENCE ONLY

Ingredients in the study formulations may variously include:

- Sunflower seed oil
- Black currant seed oil
- Bovine gelatin
- Calcium carbonate
- Glycerine
- Vitamin C (ascorbic acid)
- N-acetyl-cysteine (NAC) (antioxidant)
- Beeswax
- Fish oil (USP-Verified)
- Sunflower Lecithin
- Magnesium sulfate
- Lemon oil
- Vitamin E (d-alpha tocopherol)
- Vitamin B6 (pyridoxine-5-phosphate)
- Caramel color (MEI-4 free, gluten free; from organic cane juice)
- Titanium dioxide
- Trans-pterostilbene (plant extract from *pterocarpus marsupium*) (antioxidant)
- Vitamin A (retinyl palmitate)
- Vitamin B12 (methylcobalamin)
- Vitamin D3 (cholecalciferol)
